#### 6.4.1.7 FOLLICULAR UNIT EXTRACTION AND HISTOPATHOLOGY

Participants will be taken to the procedure room. Local anaesthesia will be injected into diseased hair-bearing area on both sides of either the axillae or groin. FUE will be performed by the investigator (who is experienced in FUE) using 0.8/0.9/1.0 mm Ertip® punch. The extracted hair follicular unit samples will have histopathological analysis to confirm complete removal of hair follicles, sebaceous glands, apocrine glands and eccrine glands. These samples are not kept for future studies and will be discarded once complete removal of the pilosebaceous units are confirmed. Participants will not be charged for samples being analysed to confirm complete removal of the pilosebaceous units.

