#### Secondary objective.

2. Comparing scores of HS severity assessments between intervention and control group at week 6, 12 and 24 after follicular unit extraction.
3. Comparing scores of HS severity assessments before and after follicular unit extraction on the treated site at week 6, 12 and 24 after follicular unit extraction.
4. To compare the number of disease flares between intervention and control group over 24 weeks.
5. To determine if specimens contain HFs, sebaceous glands, apocrine glands and eccrine glands on histopathology.

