#### 6.4.1.8 HIDRADENITIS SUPPURATIVA SEVERITY ASSESSMENT

As part of standard routine care, participants will have the Hurley Stage of their HS, nodule count and abscess count documented at baseline. This is part of standard routine care to assess whether treatment is effective, and it will also allow us to calculate the hidradenitis suppurativa clinical response (HiSCR). HiSCR is defined as a  $\geq 50\%$  reduction in inflammatory lesion count (abscesses and inflammatory nodules), and no increase in abscesses or draining fistulas when compared with baseline. Participants will also have their hidradenitis suppurativa-physician's global

assessment (HS-PGA) and International Hidradenitis Suppurative Severity Score System (IHS4) score documented in follow-up visits. Pain will be assessed using the numerical scale 30 (NRS30) pain score (See Appendix 1).

These assessments will be done at week 0, week 6, week 12 and week 24.

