## 6.7 STUDY METHODOLOGY

Participants will be taken to the procedure room. Local anaesthesia will be injected into diseased hair-bearing area on affected axillae or groin on both sides. FUE will be performed by the investigator (who is experienced in FUE) using 0.8/0.9/1.0 mm Ertip® punch. The extracted hair follicular unit samples will be analysed histologically to confirm complete removal of the pilosebaceous units. Specimens are not kept for future analysis as they will be discarded.

At each study visit, the dermatologist will count the number of abscesses and nodules (as part of standard routine care) and will document this in their medical record. This will help to also score the HiSCR, IHS4, HS-PGA4 and participants will ask to rate their pain using the numerical pain score. Scoring will be done by the principle investigator as well as another dermatologist at Sinclair Dermatology.

Participants will be given a sheet (Appendix 3) where they can complete a diary of whenever they have a flareup which will identify the date of the flareups, which side and their pain level. This will be reviewed at each study visit.

Biospecimens are not kept by the investigators and are discarded once reviewed to confirm removal of pilosebaceous units.

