## 9.3 STATISTICAL METHODS TO BE UNDERTAKEN

Abscess and nodule counts will be recorded and then compared at the study visits up to week 24. This will be done using the paired t test.

Paired t test will also be used to compare changes in HS-PGA, IHS4 and HiSCR scores between the treated and control sites.

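### The protocol does not say whether scores are regional or whole-body and nominates no region for controls, so the treated-versus-control-site comparison in section 9.3 has no defined control unit

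*Protocol*

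**What the plan says.** **Treatment.** Section 6.4.1.7 gives FUE to "both sides of either the axillae or groin". Section 6.7 says "affected axillae or groin on both sides", and the lay summary (5.1) agrees. Each treated participant therefore has one region treated, on both sides.

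**Allocation.** Section 6.6 randomises participants, not sites, 1:1 into two groups. Control participants receive topical treatment on whatever area is affected (section 6.5).

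**Objectives.** Section 6.2 contains two different comparisons. Objective 2 is between groups: "Comparing scores of HS severity assessments between intervention and control group at week 6, 12 and 24". Objective 3 is within the treated arm and specific to a site: "Comparing scores of HS severity assessments before and after follicular unit extraction on the treated site". The synopsis repeats both.

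**Analysis.** Section 9.3 plans to "compare changes in HS-PGA, IHS4 and HiSCR scores between the treated and control sites".

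**Scoring.** Section 6.4.1.8 defines HiSCR as at least a 50% "reduction in inflammatory lesion count (abscesses and inflammatory nodules), and no increase in abscesses or draining fistulas when compared with baseline". Neither this definition, nor the counting procedure in section 6.7, nor the HS-PGA and IHS4 definitions in Appendix 1, nor the schedule in Appendix 2 names a region.

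**Nearest text to a region.** The exclusion criteria (7.3) refer to target areas when ruling out candidates without terminal hairs or with previous laser hair removal. The term is not defined and is not linked to scoring. Location is recorded for flares only (section 6.3, item 6, and the Appendix 3 diary).

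**The concern.** The intervention acts on one region, but the outcomes have no stated anatomical scope. That leaves two readings, each with its own problem.

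Under whole-body scoring, disease outside the treated region enters the score as if FUE had failed to control it, and the arms may be treating different shares of the disease being scored.

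Under regional scoring, only FUE participants have an identifiable region, so there is nothing to compare it with in the controls. Investigators are unblinded and no step fixes the region before the arm is known. If the worst region were picked in the FUE arm only, regression to the mean would favour that arm.

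This matters for a pilot because sections 9.1 and 9.2 say its results will feed the sample size of later studies. An effect and SD of unknown scope serve that purpose poorly. A later analysis plan cannot recover regional counts that were never recorded, or a region that was never nominated.

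**Working it through.** **1. The plan's own figure.** 24 participants split 1:1 gives 24/2 = 12 per group, as section 9.2 states. No alpha, power, effect or SD is given, so there is no power calculation to reproduce.

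**2. Can each planned comparison be formed from what is described?**

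| Comparison | Unit needed | Described? |
|---|---|---|
| Objective 2: groups at weeks 6, 12, 24 | A participant-level score in both arms | Yes, but scope not stated |
| Objective 3: before and after on the treated site | A score for the treated region at each visit | Region exists; no regional scoring described |
| Section 9.3: treated versus control sites | A score for a treated site and for a control site | Control site not defined anywhere |

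The third row conflicts with the first. With participants randomised to parallel arms, a control site would have to be a region in a control participant, and none is nominated.

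**3. HiSCR if scoring is whole-body.** Let s be the share of baseline abscesses and inflammatory nodules outside the treated region. The protocol gives no value, so s is an assumption. Suppose those lesions do not change. If the regional count falls by a fraction r, the total falls by r(1-s). Setting r(1-s) = 0.5 gives r = 0.5/(1-s).

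| s (assumed) | Regional reduction needed |
|---|---|
| 0 | 0.5/1.0 = 50% |
| 0.2 | 0.5/0.8 = 62.5%, about 63% |
| 0.4 | 0.5/0.6 = 83% |
| 0.5 | 0.5/0.5 = 100% |

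Above s = 0.5 the reduction cannot be reached through the treated region alone. HiSCR also requires no increase in abscesses or draining fistulas. Under whole-body scoring, a net rise caused by lesions elsewhere makes a participant a non-responder even if the treated region clears.

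**4. Lesion counts and IHS4 if scoring is whole-body.** Both are sums over lesions (Appendix 1 weights nodules 1, abscesses 2, draining tunnels 4). Write the whole-body change as regional change plus outside change. If the mean outside change is the same in both arms, the between-arm difference is (regional FUE + outside) - (regional control + outside) = regional FUE - regional control. The absolute difference is unchanged, but the variance of the outside change is added.

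As an illustration, take variance proportional to lesion count and independent between regions. The variance then rises by 1/(1-s): 1.25 at s = 0.2, 1.67 at 0.4 and 2.0 at 0.5. If outside lesions add no variance the factor is 1.

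**5. HS-PGA.** This is an ordered category, so neither formula applies. Lesions elsewhere can still hold it up: on the Appendix 1 table, one remaining abscess with no inflammatory nodules scores 2, even if the treated region is clear.

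**6. When is the region chosen?** Arms are tied to participant numbers before recruitment (6.6). The number is assigned after consent (6.4.2), and FUE takes place at Visit 1 (6.4.2.2). No section says when the region is selected or whether the arm is still hidden at that point.

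**The case against.** The strongest reply is that the main comparison stands. The hypothesis (6.1), the synopsis and objectives 2 and 4 compare participant groups, and a whole-body score is a legitimate outcome for that. On this view only the word sites in section 9.3 is out of place. This is right as far as it goes: the between-group comparison can be formed. It does not supply the treated-site scores for objective 3, and it leaves the scope of every score unstated.

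It can also be said that target areas in section 7.3 apply to every candidate, so a region must be considered for controls too, and that the case report form, which is not shown, may have a region field. Both are possible. Neither is written into the scoring procedure.

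A reader might infer four stronger points that the document does not support:

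- **That whole-body scoring dilutes the effect as a matter of fact.** The protocol does not say that scoring is whole-body. Eligibility is Hurley stage 1 to 2A, disease confined to one region is possible, and at s = 0 there is no dilution.
- **That the between-arm difference shrinks by (1-s), so the required sample rises by 1/(1-s)^2.** This shrinkage applies to percentage change. For counts and IHS4, which section 9.3 and Appendix 1 treat as absolute quantities, the difference is preserved and only variance is added.
- **That the FUE region is chosen after allocation is known.** No section says so. The text only fails to prevent it.
- **That no score is tied to a region.** Objective 3 does name the treated site; what is missing is the procedure to score it.

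The HiSCR figures also assume that lesions elsewhere do not improve. Sections 6.4.1.6 and 6.5 allow treatment of flares, so the true requirement could be lower.

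**Conclusion.** The point holds in a limited form. The section 9.3 site comparison has no defined control unit and conflicts with the between-group comparison in section 6.2. Objective 3 needs treated-site scores that no described procedure collects. These two statements rest on the text alone.

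The consequences are conditional. Under whole-body scoring with outside lesions unchanged, HiSCR requires a regional reduction of between 50% (s = 0) and 100% (s = 0.5), where s is assumed. Counts and IHS4 keep their absolute difference but lose precision by an amount that depends on how variable the outside lesions are. Under regional scoring, regression to the mean is a risk only if the worst region is selected in the FUE arm alone. No sample-size multiplier should be attached to the finding.

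This does not invalidate the trial. It is a cheap correction that should be made, because the missing information cannot be reconstructed once visits have taken place.

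**What to change.** 1. At screening, before the arm is revealed, record one index region (both axillae or both groins) for every participant in both arms, and define this as the target area in section 7.3. The participant number determines the arm, so the record must precede disclosure of what the number means.
2. In sections 6.4.1.8 and 6.7 and Appendix 2, require lesion counts by region at every visit, and state the scope of each score.
3. Use index-region scores for objective 3 and for the section 9.3 comparison, with whole-body scores reported alongside.
4. Reword section 9.3 so that it compares intervention and control groups, as objective 2 does. Whether a paired test suits two independent groups is a separate question to settle in the same edit.

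The cost is one line on the screening form and a region column on the lesion count, with no extra visits. The small downside is that regional IHS4 or HiSCR is less comparable with whole-body figures from elsewhere, which is why both should be reported.

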#### 6.4.1.8 HIDRADENITIS SUPPURATIVA SEVERITY ASSESSMENT

As part of standard routine care, participants will have the Hurley Stage of their HS, nodule count and abscess count documented at baseline. This is part of standard routine care to assess whether treatment is effective, and it will also allow us to calculate the hidradenitis suppurativa clinical response (HiSCR). HiSCR is defined as a  $\geq 50\%$  reduction in inflammatory lesion count (abscesses and inflammatory nodules), and no increase in abscesses or draining fistulas when compared with baseline. Participants will also have their hidradenitis suppurativa-physician's global

assessment (HS-PGA) and International Hidradenitis Suppurative Severity Score System (IHS4) score documented in follow-up visits. Pain will be assessed using the numerical scale 30 (NRS30) pain score (See Appendix 1).

These assessments will be done at week 0, week 6, week 12 and week 24.

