Statistical Methods:	Paired t test to assess change in Hurley stage, Hidradenitis Suppurative-Physician's Global assessment score, numerical pain score, IHS4 score, HiSCR score.
Subgroups:	

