## 6. STUDY OBJECTIVES

### 6.1 HYPOTHESIS

Participants receiving FUE will have lower scores for HiSCR, HS-PGA, IHS4, NRS30 compared to those receiving standard topical resorcinol/clindamycin.

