### 6.3 OUTCOME MEASURES

1. Hidradenitis suppurativa clinical response score (HiSCR)
2. Hidradenitis suppurativa – Physician’s global assessment (HS-PGA)
3. International Hidradenitis Suppurativa Severity Score System (IHS4)
4. Pain score (NRS30)
5. Number of abscesses and nodule counts at each visit
6. Number of flare ups as well as location of flare ups

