### Appendix 3: Diary sheet for documentation of flareups.

Date of flareup	Where is the flare up (e.g. right underarm, left underarm, left groin, right groin or other)?  If other, please specify.	How would you rate this pain out of 10?

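### Pain (NRS30) is one of four scores in the between-group hypothesis, but the 30 is unexplained, section 9.3 omits pain, and the synopsis gives it only a paired t test, which cannot compare two independent arms

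*Protocol*

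**What the plan says.** The hypothesis in Protocol section 6.1 is a comparison between groups: "Participants receiving FUE will have lower scores for HiSCR, HS-PGA, IHS4, NRS30 compared to those receiving standard topical resorcinol/clindamycin". Section 6.3 lists the NRS30 pain score as the fourth of six outcome measures, without a range or derivation.

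Section 6.4.1.8 gives the only expansion of the label: "Pain will be assessed using the numerical scale 30 (NRS30) pain score", followed by a pointer to Appendix 1. It also fixes the timing: "These assessments will be done at week 0, week 6, week 12 and week 24". Appendix 1, in its title and in item e, calls the instrument a numerical rating scale (NRS), with no 30. Section 6.7 calls what participants rate at visits a numerical pain score. The glossary has entries for the other three scores in the hypothesis but none for NRS.

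Tests are assigned in two places:
- **Synopsis, Statistical Methods.** A paired t test on change in several measures, a list that ends with "numerical pain score, IHS4 score, HiSCR score".
- **Section 9.3.** A paired t test for abscess and nodule counts, and again to "compare changes in HS-PGA, IHS4 and HiSCR scores between the treated and control sites". Pain is not named.

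**The concern.** There are two linked faults.

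First, the label does not tell the analyst what the pain variable is. A number attached to a scale name could be a range, a percentage threshold or a leftover tag. A score and a response call for different summaries and run in opposite directions: lower is better for a score, higher is better for a response rate.

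Second, whatever the variable is, the protocol gives no usable analysis for the comparison it hypothesises. The section devoted to statistical methods omits pain. The section that includes it uses a test for paired observations, while the arms consist of different people.

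Pain is the only patient-reported severity score in the hypothesis, and the study is open-label. Sections 9.1 and 9.2 also say that the results will inform sample sizes for later studies. A standard deviation of a score and a response proportion are different inputs to that calculation, so the pilot should say which it will deliver.

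**Working it through.** The protocol states no effect size, standard deviation, alpha or response rate for pain, so there is no figure to reproduce. The check is a comparison of the text, followed by a look at what the stated test can do.

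**1. The label, place by place**

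| Place | Name used | What it adds |
|---|---|---|
| 6.1 | NRS30 | Expected lower under FUE |
| 6.3 | NRS30 | Nothing further |
| 6.4.1.8 | Numerical scale 30 (NRS30) | Weeks 0, 6, 12, 24; see Appendix 1 |
| 6.7 | Numerical pain score | Rated by participants at visits |
| Synopsis | Numerical pain score | Paired t test on change |
| Appendix 1, title and item e | Numerical rating scale (NRS) | Heading only; a figure in this appendix is not shown |
| 9.3 | Not mentioned | No test |

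The names without a number are compatible with one another. The 30 stands in three sections and is explained in none.

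**2. What the paired t test can answer**

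Section 6.6 allocates numbers 1 to 24 at random to two groups, and section 9.2 puts 12 in each. No participant in one arm is matched to a participant in the other.
- A paired t test of Week 24 against Week 0 can be run within one arm, with 12 − 1 = 11 degrees of freedom. It addresses the before-and-after objective in section 6.2 (item 3).
- It does not address section 6.1 or item 2 of section 6.2. A hypothetical case shows why: if mean pain falls by 1 point in both arms, each within-arm test may be significant, yet the between-arm difference is 1 − 1 = 0.
- Pairing across arms would need an arbitrary matching of participants, and the result would depend on that matching.
- Adding pain to the existing sentence in 9.3 would not help. That sentence applies the paired test to treated and control sites, but under section 6.6 the control is a separate group of people.

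A between-arm comparison of Week 24 scores adjusted for Week 0 uses all 24 participants. It estimates three terms (intercept, arm, Week 0 score), which leaves 24 − 3 = 21 degrees of freedom if nobody is lost.

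**3. Whether score or response matters (illustration under assumed inputs)**

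Assume a 0–10 rating. A fall from 3 to 2 is 1/3 = 33% and meets a 30% threshold. A fall from 8 to 6 is 2/8 = 25% and does not, although it is the larger drop. A participant with 0 at Week 0 has no percentage change.

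The simulation used 4,000 trials per scenario with 12 per arm. Its assumptions were an integer 0–10 scale, baseline mean 5 and SD 2, SD of change 2.5 and control change −0.5. Each trial was tested at two-sided 0.05 by a two-sample t test on change and by a Fisher exact test on a reduction of at least 30%.

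| Assumed extra FUE benefit | Significant by t test only | By response only | Verdicts differ |
|---|---|---|---|
| 1 point | 9.5% | 1.5% | 9.5 + 1.5 = 11.0% |
| 2 points | 24.9% | 2.2% | 24.9 + 2.2 = 27.1% |
| 3 points | 29.8% | 2.0% | 29.8 + 2.0 = 31.8% |

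This shows that the choice can matter. It does not measure an error in this protocol, because every input except the group size is assumed.

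**The case against.** The strongest reply is that this is loose wording around an ordinary pain rating. Section 6.4.1.8 points to Appendix 1, where a figure is missing from the text at hand and may well print the scale and its range. Numerical pain score and numerical rating scale are everyday names for the same thing. Where the protocol means a response rule it writes one out, as it does for HiSCR (a reduction of at least 50% in inflammatory lesions), and it writes none for pain. The choice of model is commonly left to an analysis plan, which may exist.

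Much of this stands, and it rules out several stronger readings that a reader might infer:
- *Pain is undefined.* Not supported: the Appendix 1 figure may carry the scale. Only the meaning of the 30 is open.
- *NRS30 is a 30% response, so the hypothesis points the wrong way and the t test is meaningless.* This is only one possible reading, and nothing in the text states it. It cannot be excluded by the word score alone, because section 6.1 also lists HiSCR, a response measure, among scores expected to be lower.
- *The diary is a rival definition.* It asks "How would you rate this pain out of 10" for each flare, which is a different measurement from the visit rating.
- *Pain has no test at all.* The synopsis assigns one, and 9.3 is silent rather than excluding it.
- *The analysis will be chosen after the data are seen.* An analysis plan could settle it beforehand.

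What the reply does not remove is that the protocol itself names tests in two places, that those places differ on pain, and that the one test it does name for pain does not fit the hypothesis.

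**Conclusion.** The point holds in limited form. One of the four scores in the between-group hypothesis carries an unexplained number that does not match the scale name in Appendix 1, the synopsis or section 6.7. Of the two places that assign tests, one omits pain and the other gives it a test that is valid only within an arm. No section therefore provides a valid between-arm analysis of pain.

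The label on its own would be a minor clarification. The missing comparison is the more important part, because it prevents the trial from addressing its own statement about pain. This conclusion rests on the text alone and on the arms being independent, as section 6.6 describes. The effect on the result cannot be sized from the documents. The 11% to 32% range of differing verdicts is an illustration under assumed inputs and carries no weight in the conclusion.

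**What to change.** 1. Use one name and one definition for the visit pain rating in sections 6.1, 6.3, 6.4.1.8 and 6.7, the synopsis and Appendix 1. Take the range from the scale in Appendix 1. Remove the 30, or state what it means.
2. Add pain to section 9.3 as a score, compared between arms at Week 24 with adjustment for the Week 0 score (for example by ANCOVA), and make the synopsis agree. A paired t test can stay for the before-and-after objective within the FUE arm, labelled as such.
3. If a percentage-reduction response is intended, list it as a separate outcome: a proportion for which higher is better, among participants with pain at Week 0, with the threshold stated.
4. Keep the diary rating as a per-flare record, distinct from the visit score.

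The cost is protocol wording through the usual amendment route. No new visit, instrument or participant is needed, because the rating is already planned at Weeks 0, 6, 12 and 24.
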